# Table 1.Summary of the Estimand Attributes of the Primary Efficacy
Endpoint

# 9.3.3 Sensitivity and Supplementary Analyses of the Primary Efficacy Endpoint

As supplementary analyses of the primary endpoint, the same analyses listed in Section 9.3.2 will be repeated for the ITT population following the imputation rules for the missing *Wolbachia* depletion results at Month 6 (Section 9.2).

#### 9.4 Secondary Efficacy Endpoints and Analyses

#### 9.4.1 Key Secondary Efficacy Endpoints and Analyses

There is no key secondary efficacy endpoint in Study B18-894/DNDi-TYL-01 Part 1.

#### 9.4.2 Supportive Secondary Efficacy Endpoints and Analyses

The supportive secondary efficacy endpoints include the following:

- Proportion of live female adult worms with only degenerated embryos out of all live female adult worms with either normal embryos or only degenerated embryos in the uterus per subject at Month 6;
- Proportion of live female adult worms out of all female adult worms per subject at Month 6;
- The status of each subject as without microfilariae in nodular tissue at Month 6;
- The status of each subject as without skin microfilariae at Months 3 and 6;
- The reduction in skin microfilarial density (defined as the mean number of microfilariae/mg per subject) at Months 3 and 6 compared to baseline;
- The status of each nodule that contains at least 1 live female adult worm as without *Wolbachia*, as assessed by PCR, at Month 6.

All supportive secondary efficacy endpoints will be analyzed in the ITT population using observed data. All summaries will be produced by treatment arm.

The proportion of live female adult worms out of all female adult worms in each subject at Month 6 will be calculated as a percentage per subject. The proportion of live female

adult worms with only degenerated embryos out of all live female adult worms with either normal embryos or only degenerated embryos in the uterus in each subject at Month 6 will also be calculated as a percentage per subject, excluding from the denominator any worm with an empty uterus, with oocytes only, or not evaluable. Subjects with no worm for the denominator will be excluded from this summary. The percentage per subject will be summarized with descriptive statistics (number of subjects, mean and standard deviation, median, Q1, Q3, minimum, and maximum). P-values for the pairwise comparison of each of Arms A, B, C, D with Arm E will be provided using the Mann Whitney U test for the percentage per subject.

The status of each subject as without microfilariae in nodular tissue at Month 6 will be summarized as the percentage of subjects without microfilariae in nodular tissue at Month 6. The status of each subject as without skin microfilariae or not at Months 3 and 6 will be summarized in the same way. P-values for the pairwise comparison of each of Arms A, B, C, D with Arm E will be provided using the chi-square test for the binary response per subject.

The status of each nodule that contains at least 1 live adult female worm as without *Wolbachia*, as assessed by PCR at Month 6 will be summarized as the percentage of nodules without *Wolbachia* out of all nodules. The numerator and denominator of the percentage will be a sum across all subjects in a treatment arm. For the calculation of the percentages, nodules that do not contain live adult worms will be excluded from both the numerator and denominator. P-values for the pairwise comparison of each of Arms A, B, C, D with Arm E will be provided using the alternating logistic regression as detailed in Section 9.3.2 for the binary response per nodule clustered by subject.

The reduction in skin microfilarial density at Months 3 and 6 compared to baseline will be a mean change across all subjects summarized with descriptive statistics (number of subjects, mean and standard deviation, median, Q1, Q3, minimum, and maximum). The mean skin microfilarial density at baseline, Month 3 and 6 will also be summarized. Pvalues for the pairwise comparison of each of Arms A, B, C, D with Arm E will be provided using the Mann Whitney U test for the change from baseline in skin microfilarial

density per subject. The skin microfilarial density of each subject at a given time point will be collected as the final mean density of all the available skin snips. A supplementary analysis will be performed for this endpoint including only the final mean density values from  $\geq 2$  skin snips.

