2.1 Background Information on Onchocerciasis

Onchocerciasis represents a major public health problem in affected countries with up to 1.34 million disability adjusted life years lost in 2017. This disproportionately high number is driven by disease-induced disability, and overall loss of economic productivity. The challenge for mass drug administration (MDA) programs is to eliminate transmission by periodic treatment of vulnerable populations with ivermectin. This removes microfilariae (mf) from the skin and temporarily prevents the release of mf by the adult female worm. However, mf return within 6-8 months, and control strategies delivering ivermectin on a six or 12 monthly cycle must be maintained over a 10 to 15-year period to reach elimination. Notably, MDA requires extensive logistical efforts and financial commitments. Treating entire populations requires ethical discussions and evaluations of cost-effectiveness. Success in MDA is dependent on the sustained coordination of supply logistics to ensure that treatment reaches all target recipients. Because of these challenges, interruption of transmission and disease elimination worldwide has proven more difficult than initially projected. In addition, MDA given for long periods carries the risk of resistance, described for ivermectin use in animal-health applications, together with sub-optimal response in humans.² Clearly other options are needed. According to a number of recent studies and simulations, 3-5 with the current strategies, elimination of onchocerciasis will not be feasible within the timelines of the United Nations Sustainable Development Goals, 6 i.e. 90% reduction in the number of people requiring intervention by 2030, or the previous goals set by the World Health Organization (WHO) to eliminate onchocerciasis in 80% of African countries by 2025.

New treatments are needed to improve individual clinical care for patients, reduce human suffering, achieve cure and ensure advancement toward the WHO's goal of elimination by providing additional tools to shorten the timelines for elimination.

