8.3 Ivermectin: Rescue Medication, Post-Study, Screening Failures

Ivermectin used as described in this section for rescue medication or post-study will be provided as a single oral administration at the approved dose of 150 μ g/kg bw and is not an IMP, i.e. will not be presented as over-encapsulated tablets.

When ivermectin is administered at a follow-up or early termination visit, it must be administered only after completion of the procedures scheduled at that visit, and after confirmation of last menstrual period and a negative pregnancy test. Ivermectin will be administered to subjects under fasting conditions.

Subjects who fail screening in the communities or at the investigational centre will be referred to the National Program PNLMTN-CTP for MDA with ivermectin.

8.3.1 Rescue Medication in Part 1

In Part 1, ivermectin will be administered as rescue medication at any time during the study, at the investigator's discretion, to subjects with clinically significant worsening of symptoms and/or signs related to onchocerciasis.

8.3.2 Rescue Medication in Part 2

In Part 2, ivermectin will be proposed as rescue medication to all subjects with clinically significant worsening of symptoms and/or signs related to onchocerciasis at any time during the study and/or to subjects with increased mean number of skin microfilariae at Month 18, compared to the mean number at Month 12.

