 - o praziquantelo,
 - o dexamethasone^b
 - o theophylline^c
- a. Subjects taking these medications during the study will not be included in the PP population for analysis and will be imputed as failures in analyses of the primary and secondary endpoints in the ITT population.
- b. Subjects taking these medications during the treatment period (or for 14 days before) will not be included the PP population for analysis but will not be imputed as failures in analyses of the primary and secondary endpoints in the ITT population.
- c. Subjects taking these medications during the treatment period (or for 14 days before) will be included in the PP population for analysis and will not be imputed as failures in analyses of the primary and secondary endpoints in the ITT population.

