#### 8.0 Handling of Potential Intercurrent Events for the Primary Endpoint

The primary efficacy endpoint (defined in Section 3.1) will be analyzed in the PP and ITT populations and the following methods will be used to address potential intercurrent events:

- Subjects who did not complete treatment will be excluded from the PP population (definition of completion in Section 4.0). They will be included in the ITT population.
- Subjects who took prohibited medications (Appendix B) will be excluded from the PP population. They will be included in the ITT population, but subjects who took medications with an anti-filarial or anti-*Wolbachia* effect at any time during the study will be counted as failures in the ITT population (Section 9.2).
- Subjects who withdrew due to a safety issue (premature discontinuation of study or study treatment due to an adverse event related to either study drug) will be excluded from both the PP population and the ITT population analyses if they have no count of live female adult worms (no ND6M results or no live female adult worms in the ND6M results). If the subjects had live female adult worms in the ND6M results, they will be included in both the PP population and the ITT population analyses with any missing *Wolbachia* depletion results imputed as failures (Section 9.2).
- Subjects who prematurely discontinued from the study or study treatment for reasons independent of the treatment (for example, lost to follow-up, withdrew informed consent, or due to an adverse event not related to either study drug) will be excluded from both the PP population and the ITT population analyses if they have no count of live female adult worms (no ND6M results or no live female adult worms in the ND6M results). If the subjects had live female adult worms in the ND6M results, they will be included in the PP population analysis if not all *Wolbachia* depletion results were missing and they will be included in the ITT population analysis with any missing *Wolbachia* depletion results imputed through multiple imputation (Section 9.2).

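### SAP 9.4.2 analyses Part 1 secondary endpoints as observed after prohibited antifilarial or anti-Wolbachia drugs, an undeclared departure from protocol Appendix 8 footnote a; the two documents also classify rescue ivermectin differently

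*SAP*

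**What the plan says.** **Secondary endpoints.** SAP 9.4.2 gives one rule for all Part 1 secondary endpoints: "All supportive secondary efficacy endpoints will be analyzed in the ITT population using observed data". They include "The status of each subject as without skin microfilariae at Months 3 and 6", change in skin microfilarial density, microfilariae in nodular tissue, two per-subject worm percentages and nodule Wolbachia status by PCR. Arms A to D are each compared with Arm E. The skin and nodular microfilaria statuses are tested "using the chi-square test for the binary response per subject"; density change is tested by Mann-Whitney.

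**Primary endpoint.** SAP 8.0 says that subjects who took an antifilarial or anti-Wolbachia drug "will be counted as failures in the ITT population". SAP 9.2 implements this by setting all their live female worms to Wolbachia-positive. Both sections are confined by title to the primary endpoint.

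**Protocol.** Appendix 8 Section II lists the drugs prohibited throughout the study. Footnote a, attached to that section, removes takers from the PP population "and will be imputed as failures in analyses of the primary and secondary endpoints in the ITT population". Section II exempts both post-study and rescue ivermectin. SAP Appendix B has the same list but exempts only post-study ivermectin.

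**Rescue.** Protocol 8.3.1 states: "In Part 1, ivermectin will be administered as rescue medication at any time during the study, at the investigator's discretion", for clinically significant worsening. Protocol 10.4 counts rescue as failure, but only for the Part 2 primary and key secondary endpoints.

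**Consistency.** SAP 1.0 says that its analyses agree with the protocol except where SAP 13.0 notes otherwise.

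**The concern.** The protocol has a failure rule for prohibited drugs that covers secondary endpoints. The SAP drops it for those endpoints and does not say so. The omission falls where it matters most: the skin microfilaria endpoints respond directly to ivermectin. Protocol 2.1 says that ivermectin clears microfilariae from the skin, and then: "However, mf return within 6-8 months". A dose taken during follow-up can therefore suppress the Month 3 or Month 6 snip, and that subject counts as a success for the randomised regimen.

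Non-rescue use is foreseeable. The protocol describes ivermectin mass treatment in the communities, exclusion criterion 5 is written around it, and the SAP tabulates earlier ivermectin rounds.

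At stake are the reported p-values and percentages for A to D against E on skin microfilariae, which protocol 3.1 says are evaluated during the pause before Part 2. The mismatch over rescue ivermectin also bears on the primary analysis, because the classification decides whether a rescued subject stays in the PP population.

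**Working it through.** No sample size, power or alpha in the plan depends on this point, so there is no stated figure to reproduce. The check is a comparison of rules, followed by an illustration of scale.

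**Step 1. Rules side by side (Part 1, ITT).**

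| Event | Primary (Wolbachia by worm) | Secondary, protocol | Secondary, SAP |
|---|---|---|---|
| Section II drug, including non-rescue ivermectin | Failure in both documents | Failure (footnote a) | As observed (9.4.2) |
| Rescue ivermectin | SAP: failure, since Appendix B does not exempt it. Protocol: exempt from Section II, so footnote a does not apply | No rule stated | As observed (9.4.2) |
| Post-study ivermectin | Exempt in both | Not affected | Not affected |

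The first row is a contradiction. The second is a mismatch on the primary endpoint and a protocol gap on the secondary ones. The third is harmless: post-study ivermectin follows the Month 6 procedures.

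**Step 2. Is the departure declared?** SAP 13.0 records the change of the PCR endpoint from worm to nodule and a clarification of imputation in 8.0 and 9.2. It says nothing about prohibited drugs and secondary endpoints.

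**Step 3. Unit of effect.** One subject is 1/30 = 3.3 points with 30 per arm (SAP 2.4), or 1/25 = 4.0 points with the 25 expected after drop-out.

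**Step 4. Illustration.** The documents give no Part 1 clearance or drug-use rates, so everything here is assumed. Let r be the share of an arm that took such a drug, p the clearance rate without it and c the clearance rate after it.

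- As observed: (1 − r)p + rc
- Failure rule: (1 − r)p

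Take p = 10% in Arm E and 40% in an active arm (difference 30 points), with c from 50% to 90%. Example: r = 10% in Arm E only and c = 90%. As observed, E = 0.9 × 0.10 + 0.1 × 0.90 = 18%, difference 40 − 18 = 22. Failure rule, E = 0.9 × 0.10 = 9%, difference 40 − 9 = 31.

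| r in E / active | Difference as observed (points) | Difference, failure rule |
|---|---|---|
| 0 / 0 | 30 | 30 |
| 10% / 0 | 26 to 22 | 31 |
| 0 / 10% | 31 to 35 | 26 |
| 10% / 10% | 27 | 27 |
| 20% / 5% | 22.5 to 16.5 | 30 |

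Against 30 points, the as-observed difference ranges from 16.5 to 35, that is −13.5 to +5. More use in E shrinks it, more use in the active arm inflates it, and equal use gives the same answer under both rules. The failure rule does not recover 30 either (26 to 31): it answers a different question, in which drug use is itself a failure.

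The range for c suits ivermectin. For anti-Wolbachia antibiotics the Amendment 1 rationale describes a slow microfilarial decline over about 12 months, so their effect on Month 6 skin snips would be smaller; nodule PCR status is the more exposed endpoint.

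**The case against.** **Rescue is not a breach of Appendix 8.** A reader might infer that counting clearance after rescue as success violates footnote a. It does not, because Section II exempts rescue ivermectin. Nor does the Part 2 rule in protocol 10.4 settle the matter: it is limited to the Part 2 primary and key secondary endpoints, and Part 1 has no key secondary endpoint. As-observed ITT analysis after permitted rescue is a recognised treatment-policy choice. This objection stands in full.

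**The direction of bias is not known.** A reader might also infer that rescue concentrates in Arm E and pulls the comparisons toward no effect. No document gives use by arm, treatment is blinded, and the protocol expects only a slow microfilarial decline on anti-Wolbachia treatment. This stands too.

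**Use may be rare.** Rescue needs clinically significant worsening; subjects with severe manifestations, or who need and cannot avoid ivermectin in the first 6 months, are excluded. This limits the likely size, not the inconsistency.

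**Decision weight is modest.** Protocol 10.9 names safety, Wolbachia depletion, embryogenesis and microfilarial Wolbachia among the selection inputs; skin clearance is not named, although all available data are to be used. The choice between Base and Alternative Scenario does not use these endpoints. The secondary p-values are unadjusted.

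**Footnote a might mean only key secondary endpoints**, as the title of protocol 10.4 suggests. The footnote contains no such limit, and for Part 1 the reading would leave its mention of secondary endpoints with nothing to refer to. If the sponsor intends it, the SAP should say so.

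**Conclusion.** Two points hold. First, for non-rescue ivermectin, moxidectin, doxycycline, minocycline, rifampicin and rifapentine, SAP 9.4.2 contradicts protocol Appendix 8 footnote a on the Part 1 secondary endpoints, and the departure is undeclared. Second, the documents disagree on whether rescue ivermectin is prohibited for analysis. Under the SAP a rescued subject leaves the PP population and fails on every live female worm in ITT, yet the same subject's skin result is accepted as observed. Under the protocol's list, rescue alone triggers neither consequence on the primary endpoint.

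The size cannot be stated: it is 3.3 points per affected subject in 30, in a direction set by which arm has more use. The ranges in the working rest on assumed rates and show scale only. The first point relies on reading footnote a as written. This should be corrected, but it does not undermine the primary comparison of Part 1 unless rescue proves common enough for the PP classification to matter.

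**What to change.** 1. In SAP 9.4.2, apply footnote a to the secondary endpoints. After a Section II drug, set later binary status to failure and give later density change the worst rank in the Mann-Whitney test. Say what failure means for the two worm percentages. State that the rule applies to assessments after first intake, since footnote a gives no timing. Keep the as-observed analysis as supplementary. If the sponsor prefers as-observed as the main analysis, declare the departure in SAP 13.0 with a reason.
2. Reconcile SAP Appendix B with protocol Appendix 8 Section II on whether rescue ivermectin counts as prohibited for analysis. Apply the resulting classification consistently to PP membership, the primary ITT rule and the skin microfilaria endpoints. Present any failure rule for rescue as a new analysis choice, not as restoring footnote a.

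The cost is a few sentences of SAP text and one programming flag; concomitant medication is already recorded. Microfilaria-free percentages may come out slightly lower. No clinical procedure changes.

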#### 9.5 Additional Efficacy Analyses

The additional efficacy endpoints include the following:

- The status of each subject as without *Wolbachia* in skin microfilariae or not, as assessed by PCR, at baseline (screening), Month 3, Month 6, and end of study follow-up (including premature discontinuation);
- The decline in number of *Wolbachia* (assessed by PCR) in skin microfilariae per subject at Month 3, Month 6 and end of study follow-up (including premature discontinuation) compared to baseline;
- The microfilaria levels in the cornea and anterior chamber per subject, at baseline (screening), Day 13, Month 3, Month 6, and end of study follow-up (including premature discontinuation);
- the presence, severity and clinical evolution of onchocerciasis ocular disease and onchocerciasis skin disease in each subject at baseline (screening), Day 13, Month 3, Month 6, and end of study follow-up (including premature discontinuation).

All additional efficacy endpoints will be analyzed in the ITT population using data as observed. All analyses will be descriptive summaries and will be produced by treatment arm. No statistical method will be used for any pairwise comparison between arms.

The status of each subject as without *Wolbachia* in skin microfilariae or not, as assessed by PCR, will be summarized as the percentage of subjects without *Wolbachia* in skin microfilariae for each time point.

The decline in number of *Wolbachia* (assessed by ratio of PCR copy number of *Wolbachia* signal to PCR copy number of worm signal, FtsZ/Actin ratio) in skin

microfilariae per subject will be a mean change from baseline across all subjects summarized for each post-baseline time point with descriptive statistics (number of subjects, mean and standard deviation, median, Q1, Q3, minimum, and maximum). The mean number of *Wolbachia* in skin microfilariae at baseline and post-baseline time points will also be summarized.

The microfilaria levels (motile, non-motile, and total) in the cornea and anterior chamber will both be summarized as continuous variables using descriptive statistics (number of subjects, mean and standard deviation, median, Q1, Q3, minimum and maximum) for each time point. The values from the left and the right eye will be summarized separately.

Onchocerciasis ocular disease at each time point will first be summarized as the percentage of subjects with "abnormal" results from the following examinations: frequency doubling technology perimetry; pupils, extraocular movement and eyelids (pen torch); intraocular pressure (Goldman tonometer); anterior segment (slit lamp); iris anterior chamber examination; lens/cataract examination; posterior segment (slit lamp); fundus photography; visual acuity for distance; and ocular symptoms.

Then for each of the following outcomes, the percentage of subjects will be summarized for each clinical grade at each time point: ocular itching, watering eyes, ocular pain, photophobia, eye redness, blurred vision, night blindness, conjunctivitis, limbitis, punctate opacities, sclerosing keratitis, phlyctenule-like kerato-conjunctival lesions, anterior uveitis (number of cell/field and flare), cataract, glaucoma, optic nerve edema, optic nerve atrophy, posterior uveitis, chorioretinal atrophy, eyelid, chemosis, and visual field defect. The change of clinical grade from baseline will be summarized as improvement, no change, or worsening. The outcomes of the right eye and the left eye will be combined by using the higher grade of the two. The percentage of subjects will be summarized for each change category at each post-baseline time point, as well as the last post-baseline value. The clinical grading collected by the eCRF all starts from 1 for subjects without the outcome at a visit, but for the sake of analyses, grade 0 will be applied to subjects without the

be analyzed as grade 0 and 1. If the result of a particular examination is normal, all outcomes in that examination will also be normal (grade 0).

For the outcome of visual acuity (uncorrected, corrected, and color vision), continuous measures will be collected. The mean change from baseline at each post-baseline time point will be summarized across all subjects with descriptive statistics (number of subjects, mean and standard deviation, median, Q1, Q3, minimum and maximum). The mean at baseline and each post-baseline time point will also be summarized. The values from the left and the right eye will be summarized separately.

Onchocerciasis skin disease at each time point will first be summarized as the percentage of subjects with each of the symptoms collected on the skin examination eCRF form, based on the "present/absent" question. Then for each of the symptoms, the percentage of subjects will be summarized for each clinical grade at each time point. The change of clinical grade from baseline will be summarized as improvement, no change, or worsening. The percentage of subjects will be summarized for each classeline time point, as well as the last post-baseline value. When applicable, "Sum (clinical grading)" on the eCRF form will be used as the clinical grade. Otherwise, the single grading variable will be used and will be interpreted as an ordinal scale as applicable. For each symptom, the clinical grade will start from 1, but for the sake of analyses, grade 0 will be applied to subjects without the symptom.

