- AE assessment (all reported AEs);
- physical and skin examination findings;
- vital signs;
- 12-lead ECG;
- clinical laboratory parameters: haematology, biochemistry, urine analysis;
- ophthalmological examination findings.

5.6 PK and PK/PD Endpoints in Parts 1 and 2

The PK and PK/PD endpoints are:

- ABBV-4083 and albendazole sulfoxide AUC_{tau}, C_{max}, C_{min}, CL and t_{1/2}. Time above given concentrations may also be estimated;
- the relationship between the presence or absence of *Wolbachia* in female adult worms in each subject at Month 6 with respect to ABBV-4083 and albendazole sulfoxide pharmacokinetic parameters;
- the relationship between the status of adult female worms at Month 24 with respect to ABBV-4083 and albendazole sulfoxide pharmacokinetic parameters;
- the relationship between the presence or absence of skin microfilariae at Month 24 with respect to ABBV-4083 and albendazole sulfoxide pharmacokinetic parameters;
- The relationship between the reduction in skin microfilarial density over time and ABBV-4083 and albendazole sulfoxide concentrations may be explored.

Additional relationships between the efficacy and safety endpoints and ABBV-4083 and albendazole sulfoxide concentrations may be explored.

6 Study Population

The inclusion and exclusion criteria are the same for Parts 1 and 2.

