#### 3.3 Exploratory Endpoints

The exploratory efficacy endpoints are:

- the absence of *Wolbachia* in skin microfilariae per subject by PCR at all timepoints;
- the decline from baseline in number of *Wolbachia* (assessed by PCR) in skin microfilariae per subject at all timepoints;
- microfilaria levels in the cornea and anterior chamber per subject, at all timepoints when ophthalmological assessments are performed;
- the presence, severity and clinical evolution of onchocerciasis ocular disease and onchocerciasis skin disease in each subject at all timepoints when ophthalmological or skin examinations are performed.

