#### Table 2.SAP Version History Summary

Version	Date	Summary
		• Section 3.2 and Section 9.4.2 Secondary endpoint of status of each live female adult worm as without Wolbachia assessed by PCR at Month 6 has been changed to status of each nodule containing at least one live female adult worm as without Wolbachia assessed by PCR at Month 6 due to a change in PCR data availability.
		• Section 3.4 For safety endpoints, removed physical, skin, and ophthalmological examination findings since they are summarized as the secondary efficacy endpoints.
		• Section 3.4 For safety endpoints, removed urine analysis because only abnormal results are collected.
		• Section 4.0 and Section 10.1 Updated safety analysis arms to be determined by the subject's randomized arm to align with treatment regimens under study.
		• Section 5.0 Subject disposition summary for completed protocol-specified treatment, prematurely discontinued study drug, reason for discontinuation of study drug, interruption of study drug, and reason for interruption of study drug were clarified to include summaries by study drug.
		• Section 6.0 Study drug duration categorical summary was updated to add the category of "> 14 days."
		• Q1, Q3 were added to all numerical summaries that included calculation of the median.
		• Section 7.1 and Section 9.6 For demographics and baseline characteristics, categories for number of operable sites with onchocercomata, number of palpated nodules, and number of previous ivermectin rounds were updated to be 0, 1, >1. Also, number of years resident in endemic area was added, and for summary of symptoms of onchocerciasis disease, "other" category was removed.
		• Section 7.3 Summaries of prior and concomitant procedures were removed because they are collected as text fields. Anthelmintic medications taken prior to the start of study drug were removed from the summary of concomitant medications because by definition these medications were only taken prior to start of study drug.
		• Section 8.0 and Section 9.2 Clarified the conditions which lead to data imputation.
		• Section 9.1 Clarified that no adjustment for multiple comparisons would be made.

Version	Date	Summary
		• Section 9.5 Clarified that the decline in number of Wolbachia , as assessed by PCR, would be assessed using the ratio of PCR copy number of Wolbachia signal to PCR copy number of worm signal.

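### Taking the higher-graded eye before classing change can hide new or worse disease in the other eye, in subjects who already have eye disease at baseline

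*SAP*

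**What the plan says.** SAP 9.5 lists about twenty graded ocular outcomes, among them punctate opacities, sclerosing keratitis, anterior uveitis and optic nerve atrophy. For these:

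- Change is put into three classes: "The change of clinical grade from baseline will be summarized as improvement, no change, or worsening".
- The two eyes are merged: "The outcomes of the right eye and the left eye will be combined by using the higher grade of the two".
- The unit is the subject: "The percentage of subjects will be summarized for each change category at each post-baseline time point, as well as the last post-baseline value".
- A subject without the outcome is scored 0.

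The same section treats other eye measures differently. For visual acuity, and for microfilaria levels in the cornea and anterior chamber, it says: "The values from the left and the right eye will be summarized separately".

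The endpoint being served is exploratory (SAP 3.3): "the presence, severity and clinical evolution of onchocerciasis ocular disease and onchocerciasis skin disease in each subject at all timepoints". SAP 9.5 makes it descriptive, with no comparison between arms.

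Protocol 5.5 includes "ophthalmological examination findings" among the safety and tolerability endpoints. SAP 3.4 does not. The entry for SAP version 2.0 in Section 13.0 explains that the SAP "removed physical, skin, and ophthalmological examination findings since they are summarized as the secondary efficacy endpoints". The eye findings are in fact listed in SAP 3.3 as exploratory, and 9.5 is where they are summarised.

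**The concern.** The higher grade of two eyes is a reasonable description of how bad a subject's disease is at one visit. It is a poor basis for change, because the eye that supplies the higher grade at baseline need not be the one that supplies it at follow-up. A change in the other eye leaves no trace until it overtakes the baseline maximum.

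Two things are at stake. The endpoint promises the clinical evolution of ocular disease, and the rule can lose evolution in either direction. And since the separate safety listing of eye findings was removed in favour of this section, a second eye becoming affected could go unseen in the tables that the Sponsor and the DSMB review before deciding on Part 2.

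**Working it through.** **Inputs.** From SAP 9.5: the higher-grade rule, the three change classes, grade 0 for absence, and the subject as unit. The documents give no figure to reproduce and no grade range. I therefore assume grades 0 to G and show G = 1 to 4.

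**Rule on the natural reading.** M0 = max(R0, L0) at baseline and Mt = max(Rt, Lt) at follow-up. The class is worsening if Mt > M0, improvement if Mt < M0, otherwise no change.

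**Examples (right, left).**

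| Baseline | Follow-up | M0 → Mt | Reported as | What happened |
|---|---|---|---|---|
| 2, 0 | 2, 2 | 2 → 2 | no change | new grade 2 disease in left eye |
| 2, 1 | 1, 2 | 2 → 2 | no change | one better, one worse |
| 2, 0 | 1, 1 | 2 → 1 | improvement | left eye newly diseased |
| 2, 2 | 1, 2 | 2 → 2 | no change | right eye improved |
| 1, 0 | 1, 2 | 1 → 2 | worsening | seen |
| 1, 1 | 0, 2 | 1 → 2 | worsening | worsening seen, improvement not |
| 0, 0 | 0, 1 | 0 → 1 | worsening | seen |

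**Counting patterns.** These counts weight every grade pattern equally. They are not patient frequencies.

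*New disease in a clear eye, other eye affected and stable.* Right eye fixed at a (1 to G), left eye from 0 to d (1 to G): G² patterns. The result is no change when d ≤ a, which is G(G+1)/2 patterns.

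*Eyes moving in opposite directions.* Counted by full enumeration.

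| G | New disease in clear eye: no change | Opposite moves: no change | Opposite moves: improvement | Opposite moves: worsening |
|---|---|---|---|---|
| 1 | 1 of 1 | 2 of 2 | 0 | 0 |
| 2 | 3 of 4 | 10 of 18 | 4 | 4 |
| 3 | 6 of 9 | 28 of 72 | 22 | 22 |
| 4 | 10 of 16 | 60 of 200 | 70 | 70 |

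*One eye moving by one step, the other stable.* There are G(G+1) patterns. A worsening from g to g+1 is hidden when the other eye is at g+1 or above. Summing (G − g) over g = 0 to G−1 gives G(G+1)/2, half of the patterns. An improvement from g to g−1 is hidden when the other eye is at g or above, again G(G+1)/2. The half is not spread evenly: a one-step worsening is always hidden if the moving eye has the lower grade, and never if it has the equal or higher grade.

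**Subjects starting at 0/0.** M0 = 0, so any grade above 0 in either eye gives Mt > M0 and is classed as worsening. Nothing is hidden.

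**The unstated order matters.** If the change were taken within each eye first and the larger change kept, all opposite moves would be worsening (2 of 2, 18 of 18, 72 of 72, 200 of 200). The SAP sentence does not exclude that reading, and the two readings give different tables from the same data.

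**What else would show the change?**

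- SAP 9.5 first reports the percentage of subjects with an abnormal result per examination. A subject already abnormal because of one eye stays abnormal when the second is affected.
- Visual acuity and microfilaria levels are shown by eye at all visits, but they are different measurements.
- Treatment-emergent adverse events (SAP 10.2.1) need onset no later than 30 days after the last dose. Dosing ends on Day 13, and 13 + 30 = Day 43. In the Part 1 Schedule of Events, eye examinations fall on Day 13, Month 3 and Month 6. The first is inside the window and the other two are outside it. After the window, SAP 10.2 plans only the summary of deaths and listings of all SAEs and deaths.

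**The case against.** The case for leaving the rule alone has real force.

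*Eligibility.* Hiding a change requires disease in at least one eye at baseline. Exclusion criterion 7 (Protocol 6.2) applies if either eye qualifies. It covers inflammatory eye disease, glaucoma, severe uveitis, severe keratitis, and retinal or optic nerve pathology. Optic nerve atrophy, chorioretinal atrophy and most uveitis should therefore start at 0/0, where the rule works. The plainly exposed outcomes are the milder ones, such as punctate opacities and less than severe keratitis. This stands, and it limits the reach of the problem.

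*Adverse events.* Protocol 9.3.4.2 requires an abnormality that suggests disease and is new or has progressed since screening to be reported as an adverse event, with severity graded, whatever the other eye shows. A reader might infer that SAP 9.5 is the only planned summary of eye harm; that goes too far. The adverse event tables cover the Day 13 examination, serious events are listed throughout, and acuity and microfilaria levels are by eye. What remains uncovered is non-serious graded change with onset after the adverse event window.

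*Status.* The endpoint is exploratory, descriptive and defined per subject, so a subject-level grade is not out of place. That supports the higher grade at a single visit. It does not support differencing it over time.

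*The remedy.* Classing a subject as worse if either eye worsens, and as improved only if neither does, would be asymmetric. A large improvement in one eye with a one-grade slip in the other would count as worse. This stands, and is why the fix reports by eye.

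**Conclusion.** The concern holds in a limited form. On the natural reading, in subjects with disease in at least one eye at baseline, worsening of the lower-graded eye or opposite changes can be reported as no change or as improvement whenever the higher grade does not rise. One-eye improvement can be hidden when the other eye has an equal or higher grade. No by-eye summary of the graded outcomes recovers this.

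Three stronger readings are not supported:

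- That such cases are always reported as no change. With more than two grades, some are correctly classed as worsening.
- That half of single-eye worsenings are missed. The half counts equally weighted patterns on an assumed scale; the documents give neither the grade range nor a baseline distribution.
- That the outcome is materially biased towards no change. With many subjects probably at 0/0 on most outcomes, the share affected is unknown and probably small.

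The primary hypotheses are untouched. The point carries weight because, at Months 3 and 6, SAP 9.5 is the main planned summary of non-serious graded eye changes, alongside by-eye acuity and microfilaria levels. The conclusion assumes that the maximum is taken per visit, and that grades are recorded by eye, as combining them implies.

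**What to change.** In SAP 9.5, compute change from baseline within each eye and report improvement, no change and worsening for the left and right eyes separately, as is already done for visual acuity. Optionally add the number of subjects with worsening in either eye and, as a separate count, the number with improvement in either eye. Keep the higher-grade rule for the table of grades at each visit, and say that it applies only there; this also settles the order of operations.

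The cost is one or two SAP sentences, minor programming and a few more table rows. No new data are needed if grades are recorded by eye. One downside should be acknowledged: a count of worsening in either eye gives two chances for a one-grade reading difference, so it will pick up somewhat more grading variability.
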